## 7. Population Analysis

The conventions of Section 5 of this SAP will be applied. Tables and figures will be prefixed with 14, and listings will be prefixed 16. Tables will be provided for Part 1 and Part 2 unless noted otherwise.

### 7.1.1. Subject Disposition

A summary of subject disposition will be provided using enrolled subjects. The number and percentage of subjects who were enrolled, completed the study, and are included in the Safety, Full Analysis, Per Protocol, and PK Populations will be summarized, along with the reason for exclusion from the Safety, Full Analysis, Per Protocol, and PK Populations. The number and percentage of subjects discontinuing from study, and the primary reason for discontinuation from study, will also be included in the summary.

Separate listings will be provided for the following using all subjects including screen failures:

- Informed Consent (Was Subject Reconsented (Yes, No), Date of Consent/Reconsent, Date of Advarra ICF IRB Approved Version, Protocol Version Number, Version of Consent Signed (Part 1)),
- Inclusion/Exclusion (Subject Enrolled in Study (Yes, No), Enrollment Date, Part (Part 1, Part 2), Cohort (Cohort 1, Cohort 2, Cohort 4, Cohort 4 Expansion, Cohort 5, Cohort 5 Expansion), Subject Current Screen Failure (Yes, No), Subject Previous Screen Failure (Yes, No), Previous Subject ID, category/label and text for each Inclusion Criterion Not Met and each Exclusion Criterion Met for current or previous screen failure, Screen Fail Reason for current or previous screen failure), and
- Subject Visits (Visit, Date of Visit, whether Not Done, and Reason Not Done).

Separate listings will be provided for the following using enrolled subjects:

- Analysis Populations (Yes/No for Subject Inclusion in Each Population),
- End of Treatment Surgical Excision (Date Assessment Performed, All Lesions Surgically Excised (Yes, No) with Specified Reason, if applicable, Other Assessments Performed (Yes, No) with Specified Assessments, if applicable),
- End of Study Suture Removal and Post-surgical Assessment (Visit, Sutures Removed (Yes, No), Post-surgical Assessment Performed (Yes, No), Date Assessment Performed, Clinically Significant Findings (Yes, No)),

- Follow-up Call (Date of Visit, Ongoing Adverse Event Since End of Study (Yes, No), Subject Died Since Last Visit (Yes, No), Date of Death, Cause of Death (Adverse Event, Other)), and
- Subject Disposition (Enrollment Date, Date of Last Dose of Study Treatment, Date of Discontinuation or Completion of Study, Study Treatment Discontinuation and Study Discontinuation Statuses and Reasons, Date of Last Contact, and Date and Cause of Death).

### 7.1.2. Treatment Termination

A summary of treatment termination will be provided for TL1 and TL2 using the safety population.

Descriptive statistics will be provided for the following parameters:

- Days to Necrosis where Days to Necrosis = Earliest Date of Necrosis of Lesion Specified – Treatment Start Date.
- Total Dose to Necrosis (mg) where Total Dose to Necrosis = Sum of all Actual Injection Doses (mg) including Treatment Start Date up to but not including Earliest Date of Necrosis of Lesion Specified.

Necrosed lesions are defined as treated lesions recorded in EDC as necrosed during scheduled and unscheduled Study Treatment Administration visits.

The number and percentage of subjects will be provided for the following parameters:

- Treatment Administered
- Treatment Not Applicable (TL2 only)
- Completed Treatment
- Lesion Not Necrosed
- Lesion Necrosed
- Treatment Discontinued
- Reason for Treatment Discontinuation (Adverse Event, Withdrawal of Consent, Lost to Follow-up, Death, Pregnancy, Subject Noncompliance, Sponsor Terminated Study, Investigator Decision, Other)

- Reason for Treatment Non-administration (Adverse Event, Withdrawal of Consent, Lost to Follow-up, Death, Pregnancy, Subject Noncompliance, Sponsor Terminated Study, Investigator Decision, Other) (TL2 only)

A separate listing will be provided for Treatment Termination using the Safety Population, and the listing will include TL1 Treated (Yes, No), Date of Last TL1 Treatment, Reason TL1 Treatment Not Done or Terminated (Adverse Event, Withdrawal of Consent, Lost to Follow-up, Death, Pregnancy, Subject Noncompliance, Completed Treatment, Sponsor Terminated Study, Investigator Decision, Other) with Specified Reason, TL2 Treated (Yes, No, Not Applicable), Date of Last TL2 Treatment, and Reason TL2 Treatment Not Done or Terminated (Adverse Event, Withdrawal of Consent, Lost to Follow-up, Death, Pregnancy, Subject Noncompliance, Completed Treatment, Sponsor Terminated Study, Investigator Decision, Other) with Specified Reason.

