**Table 7-1 Dose Regimen (Part 2 Cohorts 1-5)** 

#### CRO must be contacted for each subject before treatment to confirm Cohort assignment

Cohorts	W1D1	W1D2	W1D3	W1D4	W2D1	W2D2	W2D3	W2D4*		
	4 mg loading	8 mg	8 mg	Safety	8 mg	8 mg	8 mg	Safety		
Cohort 1 –										
loading dose (N=3 to 6)	If 1 TRAE SI occurs in the first 3 subjects, enroll up to 6 subjects									
(* * 5 55 5)	— If no further TRAEs SI occur, then begin enrollment into Cohort 2									
	- If	2 TRAEs SI occi	ur in 6 subjects, the	en begin enrollment	into Cohort 3					
	W1D1	W1D2	W1D3	W1D4	W2D1	W2D2	W2D3	W2D4		
Cohort 2 – No	8 mg	8 mg	8 mg	Safety	8 mg	8 mg	8 mg	Safety		
loading dose (N=3 to 6)										
	• If 1 TRAE SI occurs in the first 3 subjects, begin enrollment into Cohort 4 with 30/70 split dosing of 8mg for each treatment									
Cohort 3 – has been removed										

NOTE: Cohorts 1-2: Treatment continues until TRAE (includes TRAE SI) or significant necrosis of Target Lesion #1 as determined by Sub-SRC. If significant necrosis is determined, the current assessment is changed to an assessment-only visit, and no VP-315 is administered for the remaining days of the current Treatment Interval/Week. If the subject has an additional target lesion and a TRAE has not occurred, treatment of Target Lesion #2 may begin at D1W2 of next Treatment Interval/Week. Up to 2 target lesions may be treated. Subjects that complete two weeks of treatment and the W2D4 Safety Assessment Visit without achieving complete necrosis, should return for a Limited Safety Assessment Visit on W3D1 for further evaluation of the lesion for necrosis.

Cohort 4		Lesio	n #1 Treatmei	nt	Lesion #2 Treatment						
2-day dosing regimen	W1D1	W1D2	W1D3	W2D1		W2D1	W2D2	W2D	3	W3D1	
N=30	20/70 9	20/70 9	S a fator	I ''4. J C. C.4.		20/70 9	20/70 9	Safa4		Limited	
(10 initial/ 20 expansion)	30/70 8 mg	30/70 8 mg	Safety Limited Safety		30/70 8 mg	30/70 8 mg	g Safet	y	Safety		
Cohort 5		Lesio	n #1 Treatmer	nt		Lesion #2 Treatment					
3-day dosing regimen	W1D1	W1D2	W1D3	W1D4	W2D1	W2D1	W2D2	W2D3	W2D4	W3D1	
N=30 (10 initial/	30/70 8 mg	30/70 8 mg	30/70 8 mg	Safety	Limited Safety	30/70 8 mg	30/70 8	30/70 8 mg	Safety	Limited Safety	
20 expansion)					Salety		mg			Salety	

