### **3.6. Cohort 4 (N = 36 [10 initial / 26 expansion] at two times weekly dosing)**

Subjects receive VP-315 via once-daily dosing of 8 mg, administered on 2 consecutive days in one week (W1D1, W1D2). The planned dosing regimen is a split dose of VP-315 for all treatments. The 500 $\mu$ L (8 mg) dose is to be divided into 2 injections given at least 15 minutes and no more than 30 minutes apart, with 30% (150  $\mu$ L) administered in the first injection and the remaining 70% (350  $\mu$ L) with the second injection. Treatment for a second TL may begin on D1 of the next week (W2D1, W2D2). Each individual TL is treated for the assigned 2 days only (regardless of necrosis status). Up to 2 TLs may be treated – up to 4 total doses. Subjects with only 1 TL who complete week one of treatment without complete necrosis receive no additional treatment.

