### **3.7. Cohort 5 (N = 37 [10 initial / 27 expansion] at three times weekly dosing)**

Subjects receive VP-315 via once-daily dosing of 8 mg, administered on 3 consecutive days in one week (W1D1, W1D2, W1D3). The planned dosing regimen is a split dose of VP-315 for all treatments. The 500 $\mu$ L (8 mg) dose is to be divided into 2 injections given at least 15 minutes and no more than 30 minutes apart, with 30% (150  $\mu$ L) administered in the first injection and the remaining 70% (350  $\mu$ L) with the second injection. Treatment for a second TL may begin on D1 of the next week (W2D1, W2D2, W2D3). Each individual TL is treated for the assigned 3 days only (regardless of necrosis status). Up to 2 TLs may be treated – up to 6 total doses. Subjects with only 1 TL who complete week one of treatment without complete necrosis receive no additional treatment.

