### 7.3. Demographics and Baseline Characteristics

A summary of Demographics and Baseline Characteristics will be provided for enrolled subjects and for the analysis populations listed in Section 6 of this SAP. Baseline values will be used in summaries of parameters collected at multiple visits.

Descriptive statistics will be provided for the following parameters:

- Age (years),
- Height (cm),
- Weight (kg),
- Body Mass Index (BMI) (kg/m^2),
- Serum Tryptase (ug/L),
- Total Number of Clinically Diagnosed BCC Lesions where a Clinically Diagnosed BCC Lesion means any reported lesion with a non-missing date of clinical diagnosis of BCC,
- Total Number of Pathology Diagnosed BCC Lesions where a Pathology Diagnosed BCC Lesion means any reported lesion with a non-missing date of dermatopathology diagnosis of BCC,
- Smallest Lesion Diameter Before Biopsy (cm),
- Largest Lesion Diameter Before Biopsy (cm), and
- Duration of Disease (months) where Duration of Disease = (Treatment Start Date – Earliest Date of Dermatopathology Diagnosis of BCC) / 30.4375.

The number and percentage of subjects will be provided for the following parameters:

- Sex (Male, Female),
- Female Childbearing Potential (Yes, No),
- Race (American Indian or Alaska Native, Asian, Black or African American, Native Hawaiian or Other Pacific Islander, White, Mixed Race, Unknown or Not Reported),
- Ethnicity (Hispanic, Not Hispanic, Unknown or Not Reported),
- Fitzpatrick Skin Type (I-VI),
- Histologic Diagnosis at Screening (Micronodular, Nodular, Superficial) for TL1, TL2, NTL1, NTL2, NTL3, and

- BCC Location at Screening (Face or Neck, Clavicle or Shoulder, Arm, Chest or Abdomen, Back, Buttocks or Groin, Leg or Foot) for TL1, TL2, NTL1, NTL2, NTL3.

Separate listings using enrolled subjects will be provided for the following:

- Demographics and Baseline Characteristics (Age, Sex, Female Childbearing Potential, Race, Ethnicity, Height, Weight, BMI, Fitzpatrick Skin Type, Duration of Disease),
- Screening Clinical Evaluation (Lesion Number, Lesion Diameter (cm), Location, Date of Clinical Diagnosis, Date of Dermatopathology Diagnosis, Histologic Diagnosis),
- Screening Biopsy (Lesion Number, Biopsy Performed (Yes, No), Visit, Biopsy Date, Timing of Biopsy (Historical, At screening), Biopsy Type (Punch, Shave), Size of Punch Biopsy (2mm, 3mm, Other), Biopsy Sutures Removed (Yes, No), Date Biopsy Sutures Removed), and

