## 7.6. Administration of Study Treatment

A summary of Administration of Study Treatment will be provided using the safety population.

Descriptive statistics will be provided for the following parameters:

- Total Daily Target Volume (cc),
- Total Daily Target Dose (mg),

And for each injection (Injection 1, Injection 2) within each lesion (TL1, TL2):

- Expected Injection Volume (cc),
- Actual Injection Volume (cc),
- Expected Injection Dose (mg), and
- Actual Injection Dose (mg).

The number and percentage of subjects will be provided for the following parameters:

- Study Drug Reconstituted (Yes, No).

The summary will present injection (Injection 1, Injection 2) within lesion (TL1, TL2) within scheduled visit (W1D1, W1D2, W1D3, W2D1, W2D2, W2D3).

A separate listing will be provided using the safety population for the Administration of Study Treatment, and the listing will include the parameters described as above, as well as the following parameters (not all parameters were collected at all visits):

- Lesion (to be) Injected,
- Lesion Necrosed (Yes, No, Not Applicable),
- Injection Number (1, 2),
- Injection Administered (Yes, No),
- Reason Injection Not Administered (Adverse Event, Drug Permanently Withdrawn, Investigator Decision, Subject Declined, Other),

- Received Full Dose (Yes, No),
- Dose Received if Not Full Dose,
- Reason Full Dose Not Received (Adverse Event, Drug Permanently Withdrawn, Investigator Decision, Subject Declined, Other), and
- Visit, and Date and Time of Injection.

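### SAP 7.1.2 counts necrosis only at dosing visits and does not tie its start date or summed doses to the lesion, so the Cohort 4 and 5 necrosis rows can mislead

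*SAP*

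**What the plan says.** SAP 7.1.2 plans a treatment-termination summary for TL1 and TL2 in the safety population. It gives counts of necrosed and non-necrosed lesions and descriptive statistics for Days to Necrosis and Total Dose to Necrosis. Necrosis status is limited by visit type: "Necrosed lesions are defined as treated lesions recorded in EDC as necrosed during scheduled and unscheduled Study Treatment Administration visits". Days to Necrosis is the lesion's earliest necrosis date minus the treatment start date. Total Dose to Necrosis is "Sum of all Actual Injection Doses (mg) including Treatment Start Date up to but not including Earliest Date of Necrosis of Lesion Specified". In both formulas only the necrosis date is tied to a lesion. SAP 7.3 uses the same start-date term at subject level: "Duration of Disease = (Treatment Start Date – Earliest Date of Dermatopathology Diagnosis of BCC".

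Under SAP 3.6 and 3.7, each lesion gets 8 mg a day for two days in Cohort 4 and three days in Cohort 5, whatever its necrosis status. A subject with one target lesion gets nothing after week 1. A second lesion may start on W2D1.

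Protocol Table 7-1 makes W1D3 a Safety visit in Cohort 4 and a dosing visit in Cohort 5, whose Safety visit is W1D4. Footnote t(b) to Protocol Table 8-1 has necrosis judged at the W1 Safety Assessment in one-lesion subjects and, if it is incomplete, again on W2D1.

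SAP Section 14, which lists departures from the protocol, mentions neither the visit restriction nor the lesion-free start date.

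**The concern.** A rule that reads necrosis from dosing visits suits Part 1 and Cohorts 1 and 2, where the lesion is checked to decide whether to dose again. In Cohorts 4 and 5 the course is fixed and necrosis does not end it. There the rule removes from the table the visits at which the protocol still has necrosis assessed after the last dose.

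The cut-off falls one day later in Cohort 5 than in Cohort 4, and SAP 5.5 shows these groups in separate columns. A reader could take a difference in Lesion Necrosed, Days to Necrosis or Total Dose to Necrosis as a difference between regimens when part of it comes from the visit schedule. In the TL2 rows, part could also come from doses given into TL1. The stated purpose of these cohorts includes learning about the dosing regimen for a pivotal study, so such a misreading is worth preventing even in a descriptive table.

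**Working it through.** **Inputs.** Daily dose 8 mg; dosing days 1–2 (Cohort 4) or 1–3 (Cohort 5) from SAP 3.6 and 3.7. Visit types from Protocol Table 7-1. TL2 starts on W2D1, which is study day 8. Necrosis is assessed before that day's injection (Protocol 8.4.6 places the CRA, required for evaluating necrosis, before injection). Full doses and scheduled visits are assumed.

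**The plan's own figures.** Split dose: 2.4 + 5.6 = 8.0 mg. Maximum doses per subject: 2 lesions × 2 days = 4 (Cohort 4) and 2 × 3 = 6 (Cohort 5), both as stated. Full dose per lesion: 2 × 8 = 16 mg and 3 × 8 = 24 mg.

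**Step 1: TL1 in a one-target-lesion subject.** Days = day of necrosis − 1. Dose = 8 mg × number of dosing days before that day. A record counts only if the day is a dosing visit.

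| Necrosis first seen | Cohort 4: days, dose, counted? | Cohort 5: days, dose, counted? |
|---|---|---|
| Day 2 (W1D2) | 1, 8 mg, yes | 1, 8 mg, yes |
| Day 3 (W1D3) | 2, 16 mg, no | 2, 16 mg, yes |
| Day 4 (W1D4) | no scheduled visit | 3, 24 mg, no |
| Day 8 (W2D1) | 7, 16 mg, no | 7, 24 mg, no |

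The only values these rows can take are 1 day/8 mg in Cohort 4, and 1 day/8 mg or 2 days/16 mg in Cohort 5. The definition does include unscheduled visits, but they must still be treatment administration visits. With two target lesions, TL1 could be picked up at a week 2 dosing visit if the form allows it.

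**Step 2: TL2, formula read literally.** Days = study day of necrosis − 1. Dose = all doses into either lesion before that day. The lesion's own values use study day − 8 and TL2 doses only.

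| TL2 necrosis seen | Literal | Lesion's own |
|---|---|---|
| Cohort 4, W2D2 (day 9) | 9 − 1 = 8 days; 16 + 8 = 24 mg | 1 day; 8 mg |
| Cohort 5, W2D2 (day 9) | 9 − 1 = 8 days; 24 + 8 = 32 mg | 1 day; 8 mg |
| Cohort 5, W2D3 (day 10) | 10 − 1 = 9 days; 24 + 16 = 40 mg | 2 days; 16 mg |

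The excess is 7 days in both cohorts, 16 mg in Cohort 4 and 24 mg in Cohort 5. Because the dose excess differs, equal TL2 histories (1 day/8 mg) would show as 24 mg against 32 mg. The figures differ in Part 1 and Cohort 1, where doses vary.

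**Step 3: weight of one uncounted lesion.** In the SAP's Cohort 4 groups, with everyone in the safety population, one subject is 1/10 = 10.0 points (initial) or 1/26 = 3.8 points (expansion). The documents give neither necrosis rates nor the number of one-lesion subjects, so this is a weight per lesion and not an estimate of the effect.

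**The case against.** Four arguments stand against making much of this.

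- **The form is not shown.** The definition depends on what EDC records, and SAP 7.6 says that not every parameter was collected at every visit. Whether sites could enter necrosis status outside a dosing visit cannot be checked. This stands, so the claim must be conditional. Any display footnotes are likewise not in the text available.
- **A lesion-level start date is a possible reading.** The table is laid out by lesion, its listing gives the last treatment date for TL1 and TL2 separately, injections are recorded by lesion, and SAP 5.7 has tables independently validated. A programmer might well sum by lesion. But the SAP does not say so, and its other use of the term is per subject. The 16 and 24 mg follow from the literal text only.
- **The rule is the same for both cohorts.** Each loses necrosis first seen after its last assigned dose. That is correct, and Cohort 5's day-4 gap belongs in the description. The effect still differs at day 3, where exposure is equal.
- **Necrosis is shown elsewhere.** SAP 9.5 summarises CRA necrosis grade by lesion at the Safety and Limited Safety visits. That limits the harm, but it does not correct the counts, days or doses in 7.1.2.

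**Conclusion.** The point holds as a minor defect of specification. As written, 7.1.2 counts no necrosis after the last dosing visit in one-target-lesion subjects of Cohorts 4 and 5, so day-3 necrosis after 16 mg can be counted in one cohort and missed in the other. Read literally, the TL2 rows are 7 days too long and 16 or 24 mg too high. This rests on full dosing, scheduled visits, TL2 starting on W2D1, assessment before injection, and an EDC form that does not hold the status elsewhere.

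A reader might infer more, in three ways that the documents do not support:

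- *That the regimen comparison or an endpoint is biased.* Days and dose to necrosis are not endpoints at any level. The Cohort 4 and 5 primary endpoints are safety events and the CRA; clearance and tumor volume come from the excision visit. None uses this table, and no inferential analysis is planned.
- *That the rule works only against Cohort 4.* Cohort 5 has the same gap one day later.
- *That the reported TL2 values will be wrong.* That depends on how an ambiguous term is programmed.

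**What to change.** In SAP 7.1.2:

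1. Start both formulas at the first injection into the specified lesion, and sum only the doses given into that lesion.
2. Count necrosis recorded at Safety Assessment, Limited Safety Assessment and unscheduled visits as well as at dosing visits, where EDC holds that field.
3. Where EDC does not hold it, footnote the table: necrosis after the last dosing visit is not captured, and the Cohort 4 and 5 rows are not comparable because their visit schedules differ.

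With items 1 and 2, day-3 necrosis reads 2 days/16 mg in both cohorts, and TL2 necrosis at W2D2 reads 1 day/8 mg in both.

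The cost is a few lines of text and light programming on data already collected, with no new visits. Item 2 does not make the rows fully comparable. Necrosis arising on day 4 would be seen at W1D4 in Cohort 5 (4 − 1 = 3 days) but not until W2D1 in Cohort 4 (8 − 1 = 7 days), so a note on the differing schedules is worth keeping in either case.

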## 7.2. Protocol Deviations

Protocol deviations will be collected throughout the duration of the study. Protocol deviations will be assigned a sponsor-defined category and subcategory, and each deviation will be classified by the sponsor as major or minor.

A summary of Protocol Deviations will be provided using enrolled subjects. The total number of subject-level deviations, major and minor, number and percentage of subjects with at least one deviation, major and minor, and the number and percentage of subjects with at least one deviation categorized by category and subcategory will be included in the summary. Subjects having more than one deviation may appear in more than one category or subcategory but will be counted at most once per each category and subcategory. Category and subcategory will be displayed in order of decreasing frequency of total category count, followed by decreasing frequency of total subcategory count, and then alphabetically if tied.

A separate listing will be provided for Protocol Deviations using all subjects, and the listing will include Category (Eligibility Criteria, Informed Consent, Protocol Implementation, Safety, and possibly others), Subcategory (Laboratory Tests Not Done, Missed Assessment, Participant Does Not Meet Eligibility Criteria, Participant Received Wrong Treatment, Participant Seen Outside of Visit Window, and possibly others), Deviation Issue, Date of Issue, Date Issue Identified, and Classification (Major, Minor).

Site-level deviations will not be summarized or listed. Site-level deviations may be presented in the Clinical Study Report (CSR).

### 7.3. Demographics and Baseline Characteristics

A summary of Demographics and Baseline Characteristics will be provided for enrolled subjects and for the analysis populations listed in Section 6 of this SAP. Baseline values will be used in summaries of parameters collected at multiple visits.

Descriptive statistics will be provided for the following parameters:

- Age (years),
- Height (cm),
- Weight (kg),
- Body Mass Index (BMI) (kg/m^2),
- Serum Tryptase (ug/L),
- Total Number of Clinically Diagnosed BCC Lesions where a Clinically Diagnosed BCC Lesion means any reported lesion with a non-missing date of clinical diagnosis of BCC,
- Total Number of Pathology Diagnosed BCC Lesions where a Pathology Diagnosed BCC Lesion means any reported lesion with a non-missing date of dermatopathology diagnosis of BCC,
- Smallest Lesion Diameter Before Biopsy (cm),
- Largest Lesion Diameter Before Biopsy (cm), and
- Duration of Disease (months) where Duration of Disease = (Treatment Start Date – Earliest Date of Dermatopathology Diagnosis of BCC) / 30.4375.

The number and percentage of subjects will be provided for the following parameters:

- Sex (Male, Female),
- Female Childbearing Potential (Yes, No),
- Race (American Indian or Alaska Native, Asian, Black or African American, Native Hawaiian or Other Pacific Islander, White, Mixed Race, Unknown or Not Reported),
- Ethnicity (Hispanic, Not Hispanic, Unknown or Not Reported),
- Fitzpatrick Skin Type (I-VI),
- Histologic Diagnosis at Screening (Micronodular, Nodular, Superficial) for TL1, TL2, NTL1, NTL2, NTL3, and

- BCC Location at Screening (Face or Neck, Clavicle or Shoulder, Arm, Chest or Abdomen, Back, Buttocks or Groin, Leg or Foot) for TL1, TL2, NTL1, NTL2, NTL3.

Separate listings using enrolled subjects will be provided for the following:

- Demographics and Baseline Characteristics (Age, Sex, Female Childbearing Potential, Race, Ethnicity, Height, Weight, BMI, Fitzpatrick Skin Type, Duration of Disease),
- Screening Clinical Evaluation (Lesion Number, Lesion Diameter (cm), Location, Date of Clinical Diagnosis, Date of Dermatopathology Diagnosis, Histologic Diagnosis),
- Screening Biopsy (Lesion Number, Biopsy Performed (Yes, No), Visit, Biopsy Date, Timing of Biopsy (Historical, At screening), Biopsy Type (Punch, Shave), Size of Punch Biopsy (2mm, 3mm, Other), Biopsy Sutures Removed (Yes, No), Date Biopsy Sutures Removed), and
- Biopsy Results (Lesion Number, Visit, Biopsy Date, Biopsy Type (Punch, Shave), Location, Date of Review, Histologic Diagnosis, Specimen Gross Description).

